#### 10.4.2 Analysis of Secondary Endpoints

##### Component Alignment

Femoral components (internal rotation, valgus and anterior tilt) and tibial components (internal rotation, valgus, and posterior slope) will be summarized using descriptive summary characteristics for continuous variables. These would additionally be stratified by surgical technique within each group (CORI Navigational versus Conventional Manual Instrumentation).

### Standard Radiographic Assessment

The presence of radiographic observations: implant loosening, implant migration, and osteolysis and other pertinent radiographic findings will be summarized as counts (n) and percentages (%) by visit. These would additionally be stratified by surgical technique within each group (CORI Navigational versus Conventional Manual Instrumentation).

Radiolucent lines (mm) by zone and visit will be summarized using descriptive statistics for continuous variables. These would additionally be stratified by surgical technique within each group (CORI Navigational versus Conventional Manual Instrumentation).

### 2011 Knee Society Score (KSS)

The 2011 KSS objective, function and satisfaction scores will be summarized at the pre-operative and postoperative visits using continuous summary characteristics. For each of these 3 KSS scores, independent repeated measures Analysis of Covariance (ANCOVA) models (to account for the correlation between subjects with bilateral knees) will be used to model the change from preoperative to postoperative KSS scores as the dependent variable. As a minimum, each model will contain a group (pre-operative and postoperative) and the investigational site as a fixed term with a repeated specification for the knee. Pre-operative prognostic and demographic variables not only restricted to age, BMI and sex, but that can also be ascertained to have an impact on the KSS scores will be introduced as covariates in the final model. These covariates will be added to the model using a stepwise approach and a covariate is retained in the final model if and only if its associated p-value  $\leq 0.1$ . Model based means (adjusted means or Least Square Means, LSMeans) and corresponding standard errors associated with each change from preoperative to postoperative KSS score will be presented by group. Model based

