### CONFIDENTIAL AND PROPRIETARY

This document contains information that is confidential and proprietary to Smith & Nephew PLC and Smith & Nephew, Inc. and is intended for use only by Smith+Nephew and its manufacturer. It shall not be reproduced or copied in whole or in part, nor shall the contents be disclosed by any means without prior written permission from Smith+Nephew, nor shall anyone make any use of it that is contrary to the expressed or implied wishes of Smith+Nephew.

Clinical Protocol	Study Number: CORI.2019.06
A Prospective, Multi-center, Randomized Controlled Study to Evaluate the Safety and Effectiveness of REAL INTELLIGENCE™ CORI™ in unicondylar knee arthroplasty (UKA) Procedure	Version: 4.0-Master, 07 Sep 2022
	Page: 47 of 167

- 1 Subject receives a UKA on the index joint as a revision for a previously failed surgery, or need for complex implants, or any other implant than a standard UKA (e.g. stems, augments, or custom made devices).
- 2 Subject has been diagnosed with post-traumatic arthritis
- 3 Subject receives simultaneous bilateral UKA OR a unilateral UKA with contralateral TKA.
- 4 Subject has one or more of the following arthroplasties that are not fully healed and well-functioning, as determined by the investigator:
  - Contralateral primary TKA or UKA, however, the subject can only have one knee enrolled in the study.
- 5 Subject does not understand the language used in the Informed Consent Form.
- 6 Subject does not meet the indication or is contraindicated for UKA according to specific S+N knee system's Instructions for Use (IFU).
- 7 Subject has active infection or sepsis (treated or untreated).
- 8 Subject is morbidly obese with a body mass index (BMI) greater than 40.
- 9 Subject is pregnant or breast feeding at the time of surgery.
- 10 Subject, in the opinion of the Investigator, has advanced osteoarthritis or joint disease at the time of surgery and was better suited for an alternate procedure.
- 11 Subject currently enrolled in another orthopedic clinical trial study.

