#### CONFIDENTIAL AND PROPRIETARY

This document contains information that is confidential and proprietary to Smith & Nephew PLC and Smith & Nephew, Inc. and is intended for use only by Smith+Nephew and its manufacturer. It shall not be reproduced or copied in whole or in part, nor shall the contents be disclosed by any means without prior written permission from Smith+Nephew, nor shall anyone make any use of it that is contrary to the expressed or implied wishes of Smith+Nephew.  
 TMP-CD-05-01 Clinical Protocol - Device - Revision D; SOP-CD-05 Clinical Protocol

Clinical Protocol	Study Number: CORI.2019.06
A Prospective, Multi-center, Randomized Controlled Study to Evaluate the Safety and Effectiveness of REAL INTELLIGENCE™ CORI™ in unicondylar knee arthroplasty (UKA) Procedure	Version: 4.0-Master, 07 Sep 2022
	Page: 82 of 167

differences (and corresponding standard errors) between the CORI Navigational and Conventional manual instrumentation groups and their corresponding 95% CIs will additionally be summarized. If the p-value associated with the group term in the model is significant (i.e.  $p < 0.05$ ), then the 95% CIs corresponding to the model based differences between the CORI Navigational and Conventional manual instrumentation groups will additionally be presented.

The 2011 KSS subject expectation score will be summarized at the pre-operative and postoperative follow-up visits using descriptive characteristics for continuous variables.

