#### Forgotten Joint Score (FJS-12)

The transformed FJS-12 score (0-100) will be summarized at the postoperative visits using continuous summary characteristics. Change from preoperative to postoperative visits will also be summarized. The repeated measures ANCOVA model to account for the correlation between subjects in case of bilateral knees analogous to that specified for the 2011 KSS will be used.

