#### CONFIDENTIAL AND PROPRIETARY

This document contains information that is confidential and proprietary to Smith & Nephew PLC and Smith & Nephew, Inc. and is intended for use only by Smith+Nephew and its manufacturer. It shall not be reproduced or copied in whole or in part, nor shall the contents be disclosed by any means without prior written permission from Smith+Nephew, nor shall anyone make any use of it that is contrary to the expressed or implied wishes of Smith+Nephew.  
 TMP-CD-05-01 Clinical Protocol - Device - Revision D; SOP-CD-05 Clinical Protocol

Clinical Protocol	Study Number: CORI.2019.06
A Prospective, Multi-center, Randomized Controlled Study to Evaluate the Safety and Effectiveness of REAL INTELLIGENCE™ CORI™ in unicondylar knee arthroplasty (UKA) Procedure	Version: 4.0-Master, 07 Sep 2022
	Page: 83 of 167

preoperative to postoperative visits will also be summarized. In the case of bilateral knees, repeated measures ANCOVA models will account for correlation between subjects with bilateral knees each for the index score and VAS analogous to that specified for the 2011 KSS will be used.

The 2011 KSS, transformed FJS-12 and EQ-5D-5L scores will additionally be summarized by group (i.e. the CORI Navigational and Conventional manual instrumentation groups) and visit using descriptive statistics for continuous variables.

The Multiple Imputation (MI) missing value imputation method will be used as the imputation method for missing 2011 KSS, FJS-12, OKS, and EQ-5D-5L endpoints. Details of the MI method will be included in the SAP.

All secondary endpoints will be summarized using the FAS analysis population.

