## 11 SAMPLE SIZE JUSTIFICATION

Parratte et al.[51] looked at the effects of postoperative mechanical axis alignment on the survival of TKAs. They found that of the 398 TKAs reviewed in the paper there were 292 (73.4%) which post-operatively were defined as mechanically aligned (i.e. with a mechanical axis of  $0^\circ \pm 3^\circ$ ).

This study is designed to demonstrate superiority in the proportion of knees achieving post-operative leg alignment in the CORI Navigational group over the Conventional manual instrumentation group.

The proportion of mechanically aligned TKAs using NAVIO from a recent analysis was estimated to be 92.1% [52]. This proportion is expected to be equivalent if NAVIO was used to determine the proportion of mechanically aligned UKAs. Using these assumptions, enrollment of 63 UKAs per group will provide 80% power to show that the lower limit of the two-sided 95% confidence interval for the proportion of mechanically aligned UKAs is greater than that obtained from literature. To account for up to a 10% attrition rate in knees enrolled, 70 knees in each group (140 knees combined) will be enrolled into the randomized stage of the study. A minimum of an additional 5 subjects who will be treated with CORI directly to fulfil the learning needs of the surgeons will be enrolled at the pre-randomized study stage, thus leading to a minimum total study enrollment of 145 subjects.

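### Do the wording errors in the secondary score models of Protocol Section 10.4.2 (group label, bilateral knees, FJS-12 change) call for a change to the plan?

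*Protocol*

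**What the plan says.** Protocol Section 10.4.2 (2011 Knee Society Score) models the change from the pre-operative to the post-operative score by repeated-measures ANCOVA. The stated reason for the repeated structure is "to account for the correlation between subjects with bilateral knees", and the minimum model is that "each model will contain a group (pre-operative and postoperative) and the investigational site as a fixed term with a repeated specification for the knee". The section then asks for adjusted means by group and for differences between CORI and conventional instrumentation with confidence intervals. It adds a conditional presentation: "If the p-value associated with the group term in the model is significant", those intervals are shown again. Under EQ-5D-5L in the same section, group is spelled out: "i.e. the CORI Navigational and Conventional manual instrumentation groups".

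For FJS-12 the section says "Change from preoperative to postoperative visits will also be summarized", and that a model "analogous to that specified for the 2011 KSS will be used". Section 9.2.6 and Table 9.1.1-9-1 schedule FJS-12 at 6 weeks, 6 months and 12 months only.

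On the unit of analysis, exclusion criterion 4 in Section 7.3 says "the subject can only have one knee enrolled in the study", and Section 11 plans that "70 knees in each group (140 knees combined) will be enrolled into the randomized stage of the study".

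The SAP (v1.0, 28 August 2024) records termination on 15 May 2024 with four subjects (Section 2). It states that the protocol's analyses will not be run (7.1), marks the secondary analysis as not applicable (7.11), and lists the switch to listings as a change from the protocol (7.15).

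**The concern.** Read literally, the model sentence cannot be fitted. A change score already contains both time points, so a factor with levels before and after surgery has nothing to separate, and the randomised arm is never named as a model term although the output requires it. The repeated structure is tied to a correlation between two knees of one person, which eligibility rules out. The correlation that does exist, between three post-operative visits of one person, gets no visit term, no arm-by-visit term and no named covariance. FJS-12 inherits a change model although no baseline is collected.

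Had the trial run to 140 subjects, two analysts might have built different models from this text and reported different standard errors for the arm difference. The worst case would be three visits per subject counted as independent observations, which would make the secondary comparisons too liberal. Section 8.1 also allows data to be combined with a parallel cohort study, so the template might be carried over.

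**Working it through.** **Number of models affected.** Three KSS scores (objective, function, satisfaction) + OKS + FJS-12 + EQ-5D-5L index + EQ-5D-5L VAS = 7.

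**Knees per subject.** Section 11 takes 63 knees per group and allows 10% attrition: 63 / 0.90 = 70 per group, and 2 × 70 = 140 knees. Section 7.1 randomises 140 subjects. 140 / 140 = 1 knee per subject, in line with exclusion criteria 3 and 4. A knee identifier is therefore also a subject identifier.

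**Meaning of group.** Two readings are possible.
- Before versus after surgery: not estimable, because the dependent variable is the difference between the two.
- CORI versus conventional: estimable, and the contrast that the same paragraph asks to be reported.

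Only the second gives a model that runs. The first is a mislabel and not a competing analysis.

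**Visits.** KSS, OKS and EQ-5D-5L each give m = 3 post-operative changes per subject. The documents give no within-subject correlation ρ, so 0.3, 0.5 and 0.7 are assumed. If the three rows were treated as independent, under compound symmetry:
- design effect DE = 1 + (m − 1)ρ = 1 + 2ρ
- understatement of the standard error = 1 − 1/√DE
- true two-sided error of a nominal 5% test = 2[1 − Φ(1.96/√DE)]

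A simulation with 63 per arm, no true difference and 40,000 runs gives the comparison:

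| ρ | DE | SE understated | Independent rows: formula (simulated) | Subject (= knee) as cluster: simulated | One visit at a time: simulated |
|---|---|---|---|---|---|
| 0.3 | 1.6 | 20.9% | 12.1% (12.2%) | 5.2% | 5.2% |
| 0.5 | 2.0 | 29.3% | 16.6% (16.4%) | 5.0% | 4.9% |
| 0.7 | 2.4 | 35.5% | 20.6% (20.5%) | 4.9% | 5.0% |

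The inflated column belongs to an analysis that ignores repetition. The protocol calls for a repeated-measures model with the knee as the repeated unit. Given one knee per subject, that is the clustered column. Fitting each visit separately also holds the level.

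**FJS-12.** Pre-operative records = 0 by design (Sections 9.1.2 and 9.2.6, Table 9.1.1-9-1), so 0 of 3 planned changes can be computed, and multiple imputation has no observed baseline to work from. Section 10.4.2 separately specifies summaries of the post-operative score, and again by arm and visit; these are feasible.

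**What the SAP leaves in force.** Of the 7 models, none is to be fitted (SAP 7.1, 7.11, 7.15).

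**The case for a change.** The strongest case for acting is that all three slips stand in the current protocol and the SAP repairs none of them. Section 10 calls itself a brief description to be completed by the SAP, and the SAP's secondary-analysis section is empty, so Section 10.4.2 remains the only modelling text. The remedy would be a few words. There is also a technical point: a repeated term on the knee protects the error rate only if the covariance structure allows correlation between rows, and none is named. A diagonal structure would bring back the inflated column.

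The textual part of this stands: the group label is wrong, the bilateral-knee rationale is redundant, and the FJS-12 change sentence is a leftover. The amendment table in Section 22.1.4 shows that the pre-operative FJS-12 summary was removed at version 3.0, while the change sentence was not.

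The rest does not carry. A diagonal covariance would defeat the purpose stated for the repeated term, which is to account for correlation. Naming the structure and adding visit terms is ordinary SAP content, which Section 8.5.4 defers to the SAP, and the protocol offers its terms only as a minimum. The SAP is empty here because the analyses were withdrawn, not because the gap was overlooked. As for pooling, Section 8.1 only permits it, neither document contains a pooling plan, and the parallel study's eligibility rules and models cannot be seen here. How this template would behave there cannot be judged.

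**Conclusion.** No change is called for. Section 10.4.2 contains a mislabelled factor, a redundant rationale and one FJS-12 analysis that cannot be run. The first two are harmless once the section is read as a whole. The third would be met by analysing the post-operative scores that the section already asks to be summarised. No inflation of type I error is shown for the model as described: 4.9% to 5.2% with the subject as the unit, under assumed correlations of 0.3 to 0.7.

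The effect on this trial is nil. These are secondary endpoints, so the primary comparison and the sample size of 63 per group (70 after attrition) are untouched. The SAP has already withdrawn all seven models after four enrolments, which is in substance what a withdrawal note in the protocol would achieve.

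The conclusion rests on one enrolled knee per subject and on the listings-only SAP remaining in force. Anyone reusing the text elsewhere should read group as the randomised arm, ignore the bilateral-knee reason, and treat FJS-12 as a post-operative score without a change or baseline term.

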#### CONFIDENTIAL AND PROPRIETARY

This document contains information that is confidential and proprietary to Smith & Nephew PLC and Smith & Nephew, Inc. and is intended for use only by Smith+Nephew and its manufacturer. It shall not be reproduced or copied in whole or in part, nor shall the contents be disclosed by any means without prior written permission from Smith+Nephew, nor shall anyone make any use of it that is contrary to the expressed or implied wishes of Smith+Nephew.  
 TMP-CD-05-01 Clinical Protocol - Device - Revision D; SOP-CD-05 Clinical Protocol

Clinical Protocol	Study Number: CORI.2019.06
A Prospective, Multi-center, Randomized Controlled Study to Evaluate the Safety and Effectiveness of REAL INTELLIGENCE™ CORI™ in unicondylar knee arthroplasty (UKA) Procedure	Version: 4.0-Master, 07 Sep 2022
	Page: 82 of 167

differences (and corresponding standard errors) between the CORI Navigational and Conventional manual instrumentation groups and their corresponding 95% CIs will additionally be summarized. If the p-value associated with the group term in the model is significant (i.e.  $p < 0.05$ ), then the 95% CIs corresponding to the model based differences between the CORI Navigational and Conventional manual instrumentation groups will additionally be presented.

The 2011 KSS subject expectation score will be summarized at the pre-operative and postoperative follow-up visits using descriptive characteristics for continuous variables.

#### Oxford Knee Score (OKS)

The OKS (0-48) will be summarized at the preoperative and postoperative visits using continuous summary characteristics. Change from preoperative to postoperative visits will also be summarized. The repeated measures ANCOVA model to account for the correlation between subjects in case of bilateral knees analogous to that specified for the 2011 KSS will be used.

#### Forgotten Joint Score (FJS-12)

The transformed FJS-12 score (0-100) will be summarized at the postoperative visits using continuous summary characteristics. Change from preoperative to postoperative visits will also be summarized. The repeated measures ANCOVA model to account for the correlation between subjects in case of bilateral knees analogous to that specified for the 2011 KSS will be used.

#### EQ-5D-5L Score

The HRQoL Index score and VAS score will be summarized using summary statistics for continuous variables pre-operatively and at all postoperative visits. Change from

#### CONFIDENTIAL AND PROPRIETARY

This document contains information that is confidential and proprietary to Smith & Nephew PLC and Smith & Nephew, Inc. and is intended for use only by Smith+Nephew and its manufacturer. It shall not be reproduced or copied in whole or in part, nor shall the contents be disclosed by any means without prior written permission from Smith+Nephew, nor shall anyone make any use of it that is contrary to the expressed or implied wishes of Smith+Nephew.  
 TMP-CD-05-01 Clinical Protocol - Device - Revision D; SOP-CD-05 Clinical Protocol

Clinical Protocol	Study Number: CORI.2019.06
A Prospective, Multi-center, Randomized Controlled Study to Evaluate the Safety and Effectiveness of REAL INTELLIGENCE™ CORI™ in unicondylar knee arthroplasty (UKA) Procedure	Version: 4.0-Master, 07 Sep 2022
	Page: 83 of 167

preoperative to postoperative visits will also be summarized. In the case of bilateral knees, repeated measures ANCOVA models will account for correlation between subjects with bilateral knees each for the index score and VAS analogous to that specified for the 2011 KSS will be used.

The 2011 KSS, transformed FJS-12 and EQ-5D-5L scores will additionally be summarized by group (i.e. the CORI Navigational and Conventional manual instrumentation groups) and visit using descriptive statistics for continuous variables.

The Multiple Imputation (MI) missing value imputation method will be used as the imputation method for missing 2011 KSS, FJS-12, OKS, and EQ-5D-5L endpoints. Details of the MI method will be included in the SAP.

All secondary endpoints will be summarized using the FAS analysis population.

#### **10.4.3 Analysis of Other Endpoint(s)**

The analyses for other endpoints (will be summarized separately in the CORI Navigational and Conventional manual instrumentation groups).

##### Leg alignment pre- and post-cementation (CORI UKA only)

Leg alignment is classified as normal, varus deformity and valgus deformity. Shift tables to summarize the changes from pre- to post-cementation will be created.

##### CORI System Time & Cutting Time

CORI System and cutting times will be summarized using summary statistics for continuous variables. The average operating and cutting times summarized using summary statistics for continuous variables. Additionally, 95% CIs based on the t-statistic will be presented.

##### CONFIDENTIAL AND PROPRIETARY

This document contains information that is confidential and proprietary to Smith & Nephew PLC and Smith & Nephew, Inc. and is intended for use only by Smith+Nephew and its manufacturer. It shall not be reproduced or copied in whole or in part, nor shall the contents be disclosed by any means without prior written permission from Smith+Nephew, nor shall anyone make any use of it that is contrary to the expressed or implied wishes of Smith+Nephew.  
TMP-CD-05-01 Clinical Protocol - Device - Revision D; SOP-CD-05 Clinical Protocol

Clinical Protocol	Study Number: CORI.2019.06
A Prospective, Multi-center, Randomized Controlled Study to Evaluate the Safety and Effectiveness of REAL INTELLIGENCE™ CORI™ in unicondylar knee arthroplasty (UKA) Procedure	Version: 4.0-Master, 07 Sep 2022
	Page: 84 of 167

All other endpoints will be summarized using the FAS analysis population.

## 10.5 SAFETY ANALYSES

All safety analyses will be summarized separately for each of the groups (i.e. CORI Navigational and Conventional manual instrumentation groups) as follows:

- The number of adverse events will be reported by seriousness, relationship to study device and anticipation.
- The number of subjects experiencing adverse events will be summarised by seriousness, relationship to study device and anticipation.
- An overall AE summary table that will summarize as number (n) and percentages (%), the overall incidence according to subjects with at least one AE; subjects with at least one AE by worst severity (mild, moderate, or severe); subjects with at least one AE by worst outcome (resolved, ongoing/unresolved, or death); subjects with an AE that led to study discontinuation) and; subjects with at least one AE by worse relatedness to device. Other events such as SAEs, ADEs, SADEs or UADEs will also be similarly summarized using the number (n) and percentages (%).
- Incidence of device-related re-interventions that occur on-study will be summarized as number (n) and percentages as well as by type.
- A listing of device deficiencies that occur on-study will be provided.
- Knee implant revision rate will be summarized as proportions with 95% CIs estimated using exact binomial methods.

All safety endpoints will be summarized using the SAF analysis population.

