### 5.2 SECONDARY OBJECTIVE(S)

The secondary objective of this study is to generate safety and performance evidence supporting the use of CORI procedures. To assess the safety and performance of CORI up to 12 months after surgery as compared to procedures using conventional manual instruments.

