### 8.4.2 Secondary Endpoints

The following secondary endpoints have been defined for this study in order to evaluate the safety and performance of CORI in comparison with conventional manual instrumentation up to 12 months post-operatively:

- Component Alignment
- Radiographic assessment (Presence of radiolucent lines, osteolysis & implant migration)
- 2011 Knee Society Score (2011 KSS)
- Oxford Knee Score (OKS)
- Forgotten Joint Score (FJS-12)
- Five-level EuroQol five-dimensional (EQ-5D-5L) VAS & index scores

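### Safety, radiographic and component-alignment endpoints serve a comparative secondary objective but are only summarised arm by arm, so no between-arm difference or its precision is estimated

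*Protocol*

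**What the plan says.** The comparative intent is explicit. Protocol section 5.2 includes the aim "To assess the safety and performance of CORI up to 12 months after surgery as compared to procedures using conventional manual instruments". Section 8.4.2 introduces the secondary endpoints, with component alignment and radiographic assessment at the top of the list, as defined "in order to evaluate the safety and performance of CORI in comparison with conventional manual instrumentation up to 12 months post-operatively".

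The planned analyses are:

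- **Component alignment (10.4.2):** the femoral and tibial angles "will be summarized using descriptive summary characteristics for continuous variables. These would additionally be stratified by surgical technique within each group".
- **Radiographic findings (10.4.2):** loosening, migration and osteolysis "will be summarized as counts (n) and percentages (%) by visit", again split by group. Radiolucent lines get continuous summaries.
- **Safety (10.5):** "All safety analyses will be summarized separately for each of the groups (i.e. CORI Navigational and Conventional manual instrumentation groups) as follows". Adverse events and device-related re-interventions get numbers and percentages, and device deficiencies get a listing. For revision: "Knee implant revision rate will be summarized as proportions with 95% CIs estimated using exact binomial methods".
- **Patient-reported scores (10.4.2):** for the 2011 KSS, a model-based CORI versus conventional difference with a 95% CI is planned. OKS, FJS-12 and EQ-5D-5L are to be modelled in the same way.

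Section 10.1 says only in general terms that 95% CIs are produced where appropriate. SAP sections 2, 7.1 and 7.15 record that the study stopped early with four subjects enrolled and that listings replace the planned analyses.

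**The concern.** A comparative objective needs an estimate of the contrast and a statement of how precise it is. For four of the six secondary endpoints the protocol supplies both. For component alignment, radiographic findings and every safety endpoint it supplies neither, in a study whose stated purpose (section 4.3) is to demonstrate safety and effectiveness for regulatory approval. The reader would have two columns of numbers and no prespecified way to set one against the other.

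Revision carries a further, narrower risk. Two per-arm 95% CIs invite a judgement by overlap, and overlap is a stricter criterion than a 95% CI for the difference. For a harm endpoint a stricter criterion errs towards reassurance. The only between-arm rule that the protocol gives for proportions, in section 10.4.1 for the primary endpoint, is of that kind.

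**Working it through.** **1. The plan's own figure.** The only sample-size calculation (section 11) concerns leg alignment, with 92.1% versus 73.4%. The usual two-proportion formula, two-sided 5% and 80% power, uses the mean proportion (0.921 + 0.734)/2 = 0.8275:

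n = [1.96 × √(2 × 0.8275 × 0.1725) + 0.842 × √(0.921 × 0.079 + 0.734 × 0.266)]² / (0.921 − 0.734)² = [1.047 + 0.436]² / 0.0350 ≈ 63 per arm.

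Then 63/0.90 = 70. Both stated figures reproduce. No size or power is stated for any endpoint discussed here.

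**2. What each endpoint receives.**

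| Endpoint | Per-arm summary | Per-arm CI | Between-arm difference with CI |
|---|---|---|---|
| KSS, and by analogy OKS, FJS-12, EQ-5D-5L | yes | not needed | yes |
| Component alignment | yes | none | none |
| Radiographic findings | yes | none | none |
| AEs, SAEs, ADEs, re-intervention | yes | none | none |
| Device deficiencies | listing | none | none |
| Implant revision | yes | exact 95% | none |

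The overlap question can therefore arise only in the last row. In the others the gap is a missing contrast and a missing measure of precision.

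**3. Revision, illustrative counts of 9/70 CORI and 1/70 conventional (assumed).**

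- Exact (Clopper-Pearson) 95% CIs: 6.1 to 23.0% and 0.0 to 7.7%. They overlap.
- Difference: 12.86 − 1.43 = 11.43 points.
- Wilson limits: 6.91 to 22.66% and 0.25 to 7.66%.
- Newcombe lower limit: 11.43 − √[(12.86 − 6.91)² + (7.66 − 1.43)²] = 11.43 − 8.61 = 2.8.
- Newcombe upper limit: 11.43 + √[(22.66 − 12.86)² + (1.43 − 0.25)²] = 11.43 + 9.87 = 21.3.
- Fisher's exact p = 0.017.

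Smallest number of CORI events out of 70 that shows an excess:

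| Control events | Newcombe CI excludes 0 | Fisher p < 0.05 | Exact CIs separate |
|---|---|---|---|
| 0 | 5 | 6 | 9 |
| 1 | 7 | 8 | 11 |
| 2 | 9 | 10 | 13 |

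**4. How often this would matter.** Section 4.2.4 gives 5/414 = 1.2% for the predecessor system, which implies 0.012 × 70 = 0.84 expected revisions per arm. With 1.2% taken as an assumed control rate, the chance of showing an excess at 70 per arm is:

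| Assumed true CORI rate | CIs separate | Fisher | Newcombe |
|---|---|---|---|
| 5% | 0.4% | 7% | 14% |
| 10% | 15% | 48% | 61% |
| 15% | 54% | 84% | 90% |

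Direct estimation is better throughout, but for a modest excess the sample size is the main limit whichever method is used.

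**5. Who is compared.** Section 10.2 places non-randomised CORI cases from China in the safety population. The two columns of section 10.5 are therefore not a purely randomised comparison.

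**The case against.** A fair defence has several parts. Section 10 calls itself a brief description and defers detail to the SAP. Section 10.1 allows CIs where appropriate. Section 5.4 says that no claims are to be confirmed. Side-by-side descriptive safety reporting is common in trials with no power for safety, and counts and percentages by arm let a reader work out most risk differences. Four of the six secondary endpoints do have planned contrasts.

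Much of this limits the point without removing it. A general allowance for CIs names no contrast, the SAP never supplied one, and a prespecified comparison should not be left to the reader. The absence of safety power is a reason to report estimates without p-values, but not a reason to omit the estimates.

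Three stronger readings are tempting, and the documents do not support them.

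- A reader might infer that overlapping intervals would hide harm across the safety data. Only revision has an interval, section 10.5 states no overlap rule, and the counts by arm are shown. Moreover, 9/70 is 12.9%, far above 1.2%.
- A reader might apply the overlap argument to component angles. The protocol plans no CI for them, so there is nothing to overlap.
- A reader might conclude that the secondary question goes unanswered altogether. The patient-reported contrasts show otherwise.

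**Conclusion.** The point holds as a gap in the protocol's analysis plan. The objective is comparative, but for component alignment, radiographic findings and all safety endpoints no between-arm difference and no measure of its precision is specified. The different treatment of the patient-reported scores shows that the omission is not a uniform choice.

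The masking risk is confined to revision and is conditional: it arises only if someone judges by overlap. At 70 per arm the exact CIs then need 9, 11 or 13 CORI events against 0, 1 or 2, where the Newcombe interval already excludes zero at 5, 7 or 9. These counts and the true CORI rates are illustrative assumptions, and the 1.2% is a literature rate for the predecessor system used as a control rate.

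The SAP cancelled all analyses after four subjects, so no reported listing changes. The point matters for the design of protocol version 4.0 and for any reuse of its text.

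**What to change.** In protocol sections 10.4.2 and 10.5, add CORI-minus-conventional estimates with 95% CIs and without p-values:

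- **Risk differences** (Newcombe, for example) for each radiographic finding, and for subjects with any AE, any SAE, a device-related re-intervention and a revision.
- **Component alignment:** the difference in each angle, together with a contrast of accuracy or spread, such as the proportion of outliers against a prespecified tolerance. A difference in signed means is not enough, because deviations in opposite directions cancel. The literature summary in section 4.2.3 reports this pattern for the predecessor system: no significant difference in tibial slope, but fewer slope outliers in medial UKA. Use the angles measured in section 9.2.2. The list in section 10.4.2 includes internal rotation, which section 9.2.2 does not measure, so the two must be reconciled.
- **Population:** randomised treated subjects, with the non-randomised China CORI cases shown separately.

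The cost is a few lines of protocol text and, in any full analysis, some extra table columns. The downside is that intervals for rare events will be wide. Given the SAP's listings-only plan, nothing in the current report needs to be redone.
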